## BACKGROUND AND RATIONALE

Food systems have been recognised to play a major role in climate change and it was estimated that they contributed to 34% of total anthropogenic greenhouse gas emissions (GHGe) in 2015 (Crippa, 2021). A French study evaluated that food accounted for 24% of the carbon footprint of households (Barbier et al., 2019). The largest contributor of these emissions is agriculture since it represents more than two-thirds of the food system's GHGe (Barbier et al., 2019). The remaining third of the GHGe is due to transportation, consumption, industrial processes and packaging. A recent study showed that even if we were to stop fossil fuel emissions, the GHGe from food systems would not allow to stay under the targeted 1.5°C increase in global temperatures (Clark et al., 2020) highlighting the importance of cutting down agricultural GHGe. It has also been shown that the structure of our diets can be modified to reduce their carbon footprint and remain within a *"safe operating space for humanity"* as modelled by planetary boundaries (Willett et al., 2019). In particular, the reduction of meat and dairy consumption and the increase of plant-based food consumption are major levers to reduce the environmental impact of our diets (Hedenus et al., 2014; Scarborough et al., 2014).

In developed countries particularly, where meat and dairy consumption is high, a shift towards more plant-based diets has been advocated by scientists for its beneficial impacts on health and the environment (Willett et al., 2019). However, this shift may not be easily achieved by consumers (Hartmann & Siegrist, 2017). This can be explained by the fact that eating meat is associated with pleasure and has strong cultural, social and personal values in our societies (Macdiarmid et al., 2016). The reluctance to reduce meat consumption may also be associated with the lack of knowledge of the environmental footprint of meat (Hartmann & Siegrist, 2017; Macdiarmid et al., 2016). The underestimation of the GHGe of different types of foods, especially animal products, has been previously highlighted and was considered as a potential area for interventions (Camilleri, 2019). In line with this idea, studies have shown that consumers with a higher knowledge regarding the impact of human behaviours on climate change declared higher intentions to adopt environmentally-friendly behaviours (Truelove & Parks, 2012).

Environmental labels on food products have been described as potential drivers of the choice of environmentally-friendly products, as they may increase consumers' knowledge about the environmental impact of the food products allowing consumers to make more informed decisions when choosing food products (Camilleri, 2019). In addition, consumers wish to be informed about the environmental footprint of the products that they consume (Gadema & Oglethorpe, 2011). However, when presented with those labels, many consumers found them hard to understand and to use (Gadema & Oglethorpe, 2011). Yet, the use of an environmental label is directly linked to its understanding (Grunert et al., 2014). Thus, there is a need of a clear environmental label that conveys key information regarding the environmental impact of foods and that is easily understood by consumers.

Interventional studies using gold-standard design (i.e., randomised controlled trials) in realistic food purchasing environments are needed to demonstrate the effect of environmental labels on food choices (Vyth et al., 2012). Supermarkets are key environments to test the effect of food labelling interventions since they represented roughly 70% of the total food sales in 2019 in France (Insee, 2019). Studies testing the effect of environmental labels on food choices carried out in realistic food purchasing settings, such as online supermarkets (Muller & Lacroix, 2019), real supermarkets (Pelletier et al., 2016; Vanclay et al., 2011; Vlaeminck et al., 2014) or restaurants (Brunner et al., 2018) are scarce. To our knowledge, only one randomised controlled trial, consisting in an online food shopping task for soups, tested the effect of an environmental label on food choices (Camilleri, 2019).

We will conduct a 2-arm randomised controlled trial (with and without labels) to test the effects of an environmental label on food choices in a virtual supermarket. Participants will take part in two shopping tasks: 1/ selection of 3 products to prepare a home-made dish, and 2/ selection of a ready-to-eat dish. These two tasks will be repeated for two scenarios: 1/ participants will be asked to select the foods as they would do for a usual day (everyday scenario), and 2/ participants will be asked to select the foods for an environmentally friendly meal (environmentally-friendly scenario). This experimental design will allow to compare food choices in the presence vs. the absence of an environmental-friendly food options when explicitly asked to do so. In line with previous results showing that participants were more likely to choose pulses for a meal at a restaurant compared to a home-cooking scenario (Melendrez-Ruiz et al., 2019), we also hypothesise that it might be easier for a consumer to choose more environmentally friendly ready-to-eat dish than more environmentally friendly ingredients to cook it from scratch.

On top of the lack of knowledge regarding the link between food systems and climate change, it has been emphasized that food choice motivations are key barriers for a shift towards more plant-based diets (Grunert et al., 2014). Many criteria are considered when purchasing foods and differ among consumers. In the French population taste, price and geographical origin of products are the key declared criteria influencing food choice (European Commission. Directorate General for Health and Food Safety, 2020). Environmental considerations such as the carbon footprint were poorly rated among food choice motives by UK supermarket shoppers (Gadema & Oglethorpe, 2011). Similarly, the environment was declared by only 15% of European respondents as an important driver influencing food choice (European Commission. Directorate General for Health and Food Safety. et al., 2020). An additional aim of the present study is to investigate the relationships between food choice motives and the effect of an environmental label on food choices.

OBJECTIVES	OUTCOME MEASURES	HYPOTHESES				
	Primary objectives					
1.1 To study the effect of an environmental label on the environmental impact of ingredients and ready- to-eat dish choice in a virtual supermarket.	Mean of PEF  score for 100g of each ingredient selected and PEF score for 100g of the ready-to-eat dish in the "everyday scenario".	
 
An environmental label will lower the environmental impact of the food choices made by the participants compared to no label.
 
The effect of the environmental label will be greater when choosing a ready-to-eat dish compared to when choosing ingredients.
 
				
1.2 To investigate whether the environmental label is informative and likely to help individuals to choose environmentally friendly food options when they	Mean PEF score for 100g of each ingredient selected and PEF score for 100g of the ready-to-eat dish in the "everyday scenario" and the "environmentally-friendly scenario".	
 
The reduction of the environmental impact of the foods chosen in the "environmentally-friendly scenario" compared to the "everyday scenario" will be greater for participants in the
 
				

## **OBJECTIVES, OUTCOMES MEASURES AND HYPOTHESES**

<sup>1 PEF score is the "Product Environmental Footprint". Details regarding its calculation is described in the paragraph "Creation of an environmental score" (page 9).

are encouraged to make environmentally friendly food choices.		environmental label condition than in the no label condition.
2.1 To study the effect of an environmental label on the nutritional quality, liking, familiarity, level of process and price of ingredients and ready-to- eat dish choices in a virtual supermarket.	Secondary objectives The following variables will be calculated for the 3 ingredients (average) and for the ready-to-eat dish chosen in the "everyday scenario": FSA scores Liking Familiarity NOVA score (only for the average of the 3 ingredients) Price per calorie (continuous variables)	
 
The environmental label will have an impact on the nutritional quality (FSA score), liking, familiarity, NOVA score and price of the foods chosen by the participants.
 

2.2 To investigate the relationships between food motives and the effect of an environmental label on ingredients and ready-to- eat dish selection in a virtual supermarket.	
 
Mean PEF score for 100g of each ingredient selected and PEF score for 100g of the ready-to-eat dish in the "everyday scenario".
 
Level of ethical concern (questionnaire score)
 
	
 
The environmental label will be more effective in reducing the environmental impact of food choices in participants with higher levels of ethical concern when making food choices.
 

## EXPERIMENTAL DESIGN

[figure not shown]
This study will be a randomised controlled trial with two experimental arms:

[figure not shown]
- 1/ No label (no label condition)
- 2/ Environmental label (label condition)

A 2-block randomisation sequence (male and female) of 1:1 will be generated to allocate each participant to one of the experimental arm before recruitment using the Random Allocation software (Saghaei, 2004).

Each participant will be asked to perform two hypothetical shopping tasks in a virtual shopping environment, first in an "everyday scenario": 1/ choice of 3 ingredients for an everyday home-cooked dish among 66 products, 2/ choice of a ready-to-eat dish for an everyday meal among 30 products. The order of presentation of the two tasks will be counterbalanced. Then, the participants will be asked to perform the same two tasks while choosing foods for a dish that is "good for the planet" ("environmentally-friendly scenario"). For a given participant, the order of presentation of the two tasks will remain the same as in the everyday scenario.

The experimental design is described **Figure 1**.

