## PARTICIPANTS AND RECRUITMENT

### Recruitment

Participants will be recruited thanks to the "PanelSens" database from the "Chemosens" platform. This database was declared to the relevant authority (*Commission Nationale Informatique et Libertés; CNIL;* n°1,148,039). Participants will be invited to take part in a lab study that aims to study food choices in a virtual supermarket. After completing the study, participants will receive a 10-euro voucher.

The recruitment will be stratified on sex:

- 50% male
  - o 50% female

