## Definition of the population for analysis

Participants who will be included in the statistical analyses are the ones having completed the shopping tasks and answered all of the questionnaires. Aim-guessers will be excluded in the sensitivity analysis.

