## Participant's characteristics

Participants' characteristics, overall and for each condition, will be displayed in a table. We will include gender, age, highest educational qualification, current employment, number of people living in the household, the perceived financial status of the household, dieting status and BMI. Continuous variables will be summarised using means and standard deviations. Categorical variables will be summarised using counts and percentages.

Objective	Dependent variables (Y)	Independent variables (x)	Data used	Statistical analysis
1.1. To study the effect of an environmental label on the environmental	Mean of PEF scores for 100g of each ingredient selected and PEF score for 100g of the ready- to-eat dish.	- Environmental label (0= no / 1= yes)	Only data from scenario 1 ("everyday scenario")	Mixed model analysis with random effect of participants. PEF = label (0/1) + type_of_food (I/RTEd) + label*type_of_food

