### Primary analyses

**MODEL 1.1:** Mixed model analysis will be used to test the effect of *labelling* (categorical variable: yes or no), *type\_of\_food* (categorical variable: ingredients or ready-to-eat dish) and *labelling\* type\_of\_food interaction* on PEF scores in the "everyday scenario", with random effect of participants to account for correlation between repeated measures. If the *labelling\*type\_of\_food interaction* is not significant, it will be removed from the model.

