### Sensitivity analyses

- Sensitivity analysis will be carried out to analyse if the results found for MODEL 1.1. remain the same when aim guessers are excluded.
- **MODEL 1.1.** will be adjusted for age, sex, level of education and BMI.
- **MODEL 1.1.** (raw and adjusted) will be replicated for the GHGe from the Agribalyse database instead of the PEF score.

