### Sample size

We powered primary analyses in order to detect a d=0.50 effect size of labelling on PEF scores based the results of a previous randomised control trial that tested the effect of an environmental label on food choices (Camilleri, 2019). A sample size of 122 participants will be required for 80% power at  $\alpha$  = 0.05 (SAS 9.4). We will recruit a sample of 130 participants to account for potential data loss due to technical problems.

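### Randomisation is stratified by sex but primary Model 1.1 omits sex; adding it is a small efficiency gain, not the correction of an error

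*Combined protocol and SAP*

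**What the plan says.** On allocation, the Experimental design section states: "A 2-block randomisation sequence (male and female) of 1:1 will be generated to allocate each participant to one of the experimental arm". No block size is given. The Recruitment section adds "The recruitment will be stratified on sex", with half men and half women. It also says that gender, like age and household structure, might influence food choice, but puts no figure on this.

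On analysis, the overview table gives Model 1.1 as "PEF = label (0/1) + type_of_food (I/RTEd) + label*type_of_food", and Primary analyses fits it "with random effect of participants to account for correlation between repeated measures". Neither place has a sex term. Under Sensitivity analyses, Model 1.1 "will be adjusted for age, sex, level of education and BMI"; this is the only place where sex enters it.

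The first hypothesis under objective 1.1 is "An environmental label will lower the environmental impact of the food choices made by the participants compared to no label". The Sample size section powers the trial for this label effect at d = 0.50, with 122 participants for 80% power and no covariate, and continues: "We will recruit a sample of 130 participants to account for potential data loss due to technical problems". The analysis population is completers only: "Participants who will be included in the statistical analyses are the ones having completed the shopping tasks and answered all of the questionnaires".

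**The concern.** The label effect compares different people, so its precision depends on variation between participants. If men and women differ in mean PEF, balancing the arms within sex reduces the true sampling variance of the label estimate. A model without sex does not register that reduction and still counts the sex difference as error. Its standard error is then slightly too large, its confidence interval slightly too wide, and its test slightly conservative. Without close balance within sex, the standard error is correct on average but larger than it needs to be.

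At stake is some power for the first hypothesis of objective 1.1. The sex-adjusted sensitivity analysis does not recover it, because a sensitivity analysis does not decide the primary hypothesis. That analysis also brings in three other covariates, among them BMI, for which the plan trims implausible values, so its sample could be smaller.

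**Working it through.** **Inputs from the plan.** d = 0.50; alpha 0.05 (taken as two-sided, since sidedness is not stated); 122 participants required and 130 recruited; 1:1 allocation; equal numbers of men and women.

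**Assumptions.** R², the share of the within-arm variance of participant-mean PEF explained by sex, is set at 0, 0.02, 0.05 or 0.10. The SD of participant means within arm is 1, and d is expressed on that SD. With equal numbers of men and women, the male-female gap is 2√R² SD: 0, 0.28, 0.45 and 0.63. The last exceeds the label effect itself, so R² = 0.10 is an upper end.

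**The plan's own figure.** The two-sided normal formula gives 2 × (1.960 + 0.842)² / 0.50² = 62.8, so 63 per arm and 126 in all. The noncentral t gives 128. The stated 122 therefore does not reproduce exactly at d = 0.50; its power is 78.2% (t) or 78.9% (normal), and 130 gives 80.8% (t). An unrounded d of about 0.512 to 0.515 would give 122 by the t method. This is a separate matter and does not affect the comparison below.

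**Formula with sex in the model, exact balance.** Noncentrality = d√(N/4) / √(1 − R²), with N − 3 degrees of freedom. At N = 122 the numerator is 0.50 × √30.5 = 2.761.

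| R² | Noncentrality | Power with sex, N = 122 | Power with sex, N = 130 | Reduction in SE, 1 − √(1 − R²) |
|---|---|---|---|---|
| 0 | 2.76 | 78.2% | 80.8% | 0.0% |
| 0.02 | 2.79 | 79.0% | 81.5% | 1.0% |
| 0.05 | 2.83 | 80.2% | 82.7% | 2.5% |
| 0.10 | 2.91 | 82.3% | 84.7% | 5.1% |

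**Type I error without sex, balanced arms.** The reported standard error is too large by a factor of about 1/√(1 − R²), so the true level is about 2 × [1 − Φ(1.96/√(1 − R²))]: 5.0, 4.8, 4.4 and 3.9%.

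**Simulation of both models.** There were 200,000 trials per cell (Monte Carlo SE about 0.09 points for power and 0.05 for type I error). They were analysed on participant means, which is equivalent to the label main effect in the balanced random-participant model. Balanced means equal arms within sex, with any odd participant assigned at random; unblocked means independent 1:1 draws.

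Power for balanced arms, N = 122, at R² = 0 / 0.02 / 0.05 / 0.10:
- Without sex: 78.2 / 78.5 / 78.7 / 79.3%
- With sex: 78.2 / 79.1 / 80.2 / 82.2%

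Gain in power (percentage points) from adding sex:

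| Setting | R² = 0 | 0.02 | 0.05 | 0.10 |
|---|---|---|---|---|
| Balanced, N = 122 | 0.0 | 0.6 | 1.5 | 2.9 |
| Balanced, N = 130 | 0.0 | 0.5 | 1.4 | 2.7 |
| Balanced, 130 randomised, 8 lost at random | 0.0 | 0.6 | 1.5 | 3.1 |
| Unblocked, N = 122 | -0.4 | 0.5 | 1.7 | 3.9 |
| Unblocked, N = 130 | -0.3 | 0.5 | 1.7 | 3.7 |
| Unblocked, 130 randomised, 8 lost at random | -0.4 | 0.5 | 1.8 | 3.8 |

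Simulated type I error without sex agrees with the formula when arms are balanced, including after 8 random losses (5.0 / 4.8 / 4.5 / 3.9%). It is about 5.0% at every R² when allocation is unblocked. With sex in the model it is 4.9 to 5.1% in every cell.

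**Bias.** In a further simulation (N = 120, balanced within sex, R² up to 0.15), the mean label estimate was 0.499 to 0.500 for a true 0.50, with or without sex. At R² = 0.10 the model without sex reported an SE of 0.182 against an actual 0.173.

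**Interaction.** The label by type-of-food test compares differences within a participant, so a main effect of sex cancels. Its simulated rejection rate under the null was 4.8 to 5.3% throughout.

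**The case against.** The strongest reply is that nothing is wrong: both models are valid, a sex-adjusted Model 1.1 is already planned, and the present primary model matches a sample size calculation without covariates. Every non-zero gain rests on an R² that the documents do not supply, and up to R² = 0.05 it is at most 1.8 points. With no block size stated, close balance within sex is not assured. If allocation is unblocked, the conservatism disappears and what remains is ordinary covariate adjustment, with a small loss if sex has no effect. Two of the three primary hypotheses, label by type of food and label by scenario, are within-participant contrasts and gain nothing.

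Most of this stands, and it limits the point to a modest improvement. It does not remove it. Sex is the one factor built into the allocation, no planned analysis adjusts for sex alone, and the analysis that includes it does not decide the hypothesis. The possible loss (0.3 to 0.4 points, only if unblocked and R² = 0) is small beside the gain at any modest sex effect. The objection that the terms raw and adjusted under Sensitivity analyses would become ambiguous is fair, but wording settles it.

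**Conclusion.** The point holds as an efficiency improvement. Omitting sex from Model 1.1 neither biases the label estimate nor inflates type I error. Adding sex would raise power for the label main effect by roughly 0.5 to 2 points if sex explains 2 to 5% of the variance of participant means, and by about 3 to 4 points at 10%. If sex explains nothing, the change makes no difference with balanced arms and loses 0.3 to 0.4 points with unblocked allocation. With closely balanced arms it also brings the test back to its nominal 5% level, from about 4.4% at R² = 0.05 and 3.9% at 0.10. These sizes rest on the assumed R², on d = 0.50 applying to the SD of participant means, and on how closely the arms are balanced within sex, which the plan does not document.

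**What to change.** Add sex as a fixed effect to primary Model 1.1, in both the overview table and Primary analyses, using the value under which the participant was allocated. Report Model 1.1 without sex as a sensitivity analysis, and keep the planned adjustment for age, sex, education and BMI. State which version is meant by raw in the greenhouse-gas repeat and which is used when aim-guessers are excluded. No change to the other models is proposed.

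The cost is SAP wording and one degree of freedom. Sex is known for every participant because it determines the allocation sequence, so no data are added and no missing values arise.

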## PARTICIPANTS AND RECRUITMENT

### Recruitment

Participants will be recruited thanks to the "PanelSens" database from the "Chemosens" platform. This database was declared to the relevant authority (*Commission Nationale Informatique et Libertés; CNIL;* n°1,148,039). Participants will be invited to take part in a lab study that aims to study food choices in a virtual supermarket. After completing the study, participants will receive a 10-euro voucher.

The recruitment will be stratified on sex:

- 50% male
  - o 50% female

### and on age:

- ~33% between 18 and 35 years old
- ~33% between 36 and 50 years old
- ~33% over 50 years old

This recruitment structure also aims to include a diverse sample including single participants, participants with children and participants with children that have left the house (estimated around 18 years of age) as we hypothesise that age, gender and the structure of the household may have an impact on food choice behaviour.

### Inclusion criteria

- Age ≥ 18 years old
- Responsible for a substantial proportion of household grocery shopping
- Fluent in French
- No dietary restrictions (vegetarian, vegan, allergies, intolerance, ...)
- No uncorrected eye problems
- No known symptoms of nausea and dizziness when wearing a virtual reality headset

## METHODS

## Online shopping tasks

### Shopping tasks

The experimental sessions will take place individually. After participants will have given their informed consent to take part in the experiment, they will be asked to sit down and will be equipped with a virtual reality headset. A qualified experimenter will be present to assist the participants.

The first step will consist in a test of the virtual environment so that participants can familiarise themselves with the virtual supermarket environment. Participants will be asked to navigate and test the functionalities of the virtual reality headset. This dummy supermarket will only include cosmetic products (shampoos, soaps, etc.).

Then, participants will start the shopping tasks under two scenarios. If participants are allocated to the "label condition", the label will be presented and explained to the participants prior to the shopping tasks with a pop-up message.

- For the first scenario, in the first task, we will ask the participants to navigate in the aisles of a virtual environment of 66 foods and to select 3 food items in order to prepare a home-cooked dish for an everyday meal. In the second task, the shopping environment will be composed of 30 foods and participants will be asked to select 1 ready-to-eat dish for an everyday meal. The order of these tasks will be balanced.
- 2) The second scenario will be broken down in the same two tasks. We will keep the same order for the two tasks as in the first scenario. This time we will ask the participants to choose foods for a meal that is "good for the planet".

